11. APPENDICES

11.1. Appendix 1: Serious Adverse Event Reporting

CONTACT THE SOFIE BIOSCIENCES, INC. MEDICAL MONITOR WITHIN 24 HOURS OF LEARNING OF ANY SERIOUS ADVERSE EVENT. IF THE SERIOUS ADVERSE EVENT IS FATAL OR LIFE THREATENING, THE SPONSOR MUST BE INFORMED IMMEDIATELY.

For reporting of serious adverse events, Investigators must enter the SAE report form into database within 24 hours to the following:

To discuss SAE with the Medical Monitor, contact <TBD>> at the numbers provided below: Name: TBD
Office #: TBD Cell #: TBD Email: TBD

All reports of SAEs should be entered into the database within one working day. Follow-up information to SAEs must also be entered into the database within 24 hours as it becomes known **to the investigator**.

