5.2.4. Safety endpoints

- Incidence and severity of TEAEs or TSEAEs 24 hours from [^{68}Ga]FAPI-46 administration according to MedDRA/CTCAE V.5.0.

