7.2. Adverse Events

7.2.1. Collection Window

For the purposes of this study, the adverse event collection window is from the time of injection with [⁶⁸Ga]FAPI-46 through 24 hours post-injection. If the 24 hour window ends on a holiday or non-clinic day (or the participant cannot return to clinic due to unforeseen circumstances, such as weather), the window may be extended until 72 hours post-injection.

Adverse event collection windows are tied to the number of [⁶⁸Ga]FAPI-46 injections. Cohort 1 will have one AE collection window whereas Cohort 2 will have two discrete AE collection windows.

Any adverse event suspected to be related to [⁶⁸Ga]FAPI-46 – regardless of collection window – should be assessed and reported to the Sponsor/CRO

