7.2.3. Reporting Adverse Events

- **Routine adverse events**

Adverse events that do not meet serious criteria (section 8.4) are considered routine adverse events. Routine adverse events are reported utilizing the appropriate eCRF page in the study database.

The investigator is reminded to comply with all institutional and local requirements as well as the requirements put forth by the IRB of record regarding reporting of routine adverse events.

- **Serious adverse events**

Any adverse event meeting serious criteria (section 8.2) occurring within the collection window must be reported following the instructions in Appendix 1 – Serious Adverse Event Reporting. **The timeframe for reporting** the event to the sponsor/CRO is **1 business day** of the clinical investigator becoming aware of the initial event or clinically significant follow-up information.

The Investigator must provide a causality assessment and must sign and date all SAE Report Forms.

If supporting documentation is included in the submission (e.g., hospital reports, consultant reports, death certificates, autopsy reports, etc.), all protected health information must be redacted. When appropriate, additional written reports and supporting documentation will be provided by the site for further clarification and information.

The investigator is reminded to comply with all institutional and local requirements as well as the requirements put forth by the IRB of record regarding serious adverse events.

- **Adverse events leading to study discontinuation**

Participants who have withdrawn, or were withdrawn, from the study due to an adverse event (regardless of attribution) will be followed by the investigator until resolution or a new baseline, provided the participant consents to being followed.

- **Attribution to Investigational Medical Product and Study Procedure**

The relationship of [⁶⁸Ga]FAPI-46 and the PET scan procedure to an adverse event will be assessed by the Investigator utilizing the FDA's December 2012 guidance *Safety Reporting Requirements for INDs and BA/BE Studies*.

The investigator must note if there is a reasonable possibility there is evidence to suggest a causal relationship between [⁶⁸Ga]FAPI-46 and the adverse event and if there is evidence to suggest a causal relationship between the PET scan procedure and the adverse event.

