8.2. Safety Analysis

All patients who receive any amount of [⁶⁸Ga]FAPI-46 will be included in the final summaries and listings of safety data.

Frequencies of patients experiencing at least one AE will be displayed by body system and preferred term according to MedDRA terminology. Detailed information collected for each AE will include: description of the event, duration, whether the AE was serious, intensity, relationship to study drug, action taken, clinical outcome, and whether or not it was a DLT. Intensity (severity) of the AEs will be graded according to the CTCAE v4.0. Emphasis in the analysis will be placed on AEs classified as dose limiting.

Summary tables will present the number of patients observed with AEs and corresponding percentages. The denominator used to calculate incidence percentages consists of patients receiving at least one dose of study medication. Within each table, the AEs will be categorized by MedDRA body system and preferred term. Additional subcategories will be based on event intensity and relationship to study drug.

Deaths and other SAEs will be tabulated.

Vital signs will be summarized using descriptive statistics.

Summary tables will be prepared to examine the distribution of laboratory measures over time.

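### The SAP counts every recorded adverse event as treatment-emergent, so late serious events, whose reporting scope differs between Protocol 7.2.3 and Appendix 1, enter a 24-hour safety endpoint

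*Protocol*

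**What the plan says.** Protocol 7.2.1 runs the collection window from injection "through 24 hours post-injection. If the 24 hour window ends on a holiday or non-clinic day" (or the participant cannot return), in which case "the window may be extended until 72 hours post-injection". Cohort 2 has two such windows, one per injection. The same section makes an exception for any event suspected to be related to the tracer, which "regardless of collection window – should be assessed and reported to the Sponsor/CRO".

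Protocol 7.2.3 sets the duty for serious events: "Any adverse event meeting serious criteria (section 8.2) occurring within the collection window must be reported following the instructions in Appendix 1".

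Appendix 1 asks sites to contact the medical monitor "WITHIN 24 HOURS OF LEARNING OF ANY SERIOUS ADVERSE EVENT" and adds "All reports of SAEs should be entered into the database within one working day". It neither repeats the window nor says that it widens it.

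The safety endpoint in Protocol 5.2.4 is "Incidence and severity of TEAEs or TSEAEs 24 hours from" administration of the tracer. Protocol 8.2 says "Deaths and other SAEs will be tabulated", with no period given.

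SAP 10.7.1 restates the collection window. It then classes every collected adverse event as treatment-emergent and puts everything recorded in the eCRF into the TEAE summaries. SAP Table 1 states the safety endpoint without the 24-hour limit, and SAP Section 8, which lists changes from the protocol, does not mention this.

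**The concern.** The text a site uses to file an SAE is worded more broadly than the text that creates the duty to file it. A site that follows 7.2.1 and 7.2.3 would not file an unrelated post-operative SAE; a site that takes Appendix 1 literally would. Both will often know of the event, because they capture neoadjuvant treatment and surgery and review charts for outcomes for 14 days after surgery.

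The statistical consequence comes from the SAP. Without an onset filter, whatever was entered is counted. The serious and fatal TEAE rows could then mix events from the first day after injection with surgical or neoadjuvant events weeks later, and the mix could depend on how each site read the protocol. A reader would take those rows as the 24-hour endpoint of Protocol 5.2.4.

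**Working it through.** The plan states no figure to reproduce. The check sets the texts side by side by class of SAE, then compares the lengths of time involved.

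| Class of SAE | Protocol 7.2.1 and 7.2.3 | Appendix 1, read literally | SAP 10.7.1, if entered | Within the 24 hours of 5.2.4? |
|---|---|---|---|---|
| Onset within 24 h of an injection | Report | Report | Serious TEAE | Yes |
| Onset 24 to 72 h, window extended | Report | Report | Serious TEAE | No |
| Onset after the window, suspected related | Report (7.2.1) | Report | Serious TEAE | No |
| Onset after the window, not suspected related | Not required | Report | Serious TEAE | No |

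Two results follow.

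1. The protocol texts part company only in the last row. That is where collection can differ by site.
2. The SAP departs from 5.2.4 in the last three rows. This does not depend on how Appendix 1 is read: a late suspected-related SAE, properly reported under 7.2.1, would also be counted.

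Length of time, from the documents:

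- Pre-surgical scan to surgery: up to 21 days (Protocol 6.1).
- Chart review after surgery: 14 days (Protocol 6.1 and 1.3).
- Total: 21 + 14 = 35 days, and 35 × 24 = 840 hours.
- Share covered by the standard window: 24 / 840 = 2.9%.
- Share covered by the extended window: 72 / 840 = 8.6%.

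In Cohort 2 the neoadjuvant period lies between the two windows. Its length is not stated, so it is left out of the 35 days.

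The window is not always free of surgery. A footnote to the Cohort 1 schedule allows surgery less than 24 hours after injection under a stated condition. The split must therefore be made on onset time, not on the presumed cause of the event.

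Effect of one patient: if 60 patients are treated, each patient with only an out-of-window SAE adds 1 / 60 = 1.7 percentage points to the overall serious TEAE percentage. The step is larger in by-cohort tables, whose denominators are smaller.

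**The case against.** The strongest reply is that there is one rule, not two. Section 7.2.3 says which SAEs to report and sends those events to Appendix 1 for instructions, so the appendix can be read as procedure only. The rest of the plan fits this. The adverse event rows of the Schedules mark only the scan and follow-up visits, with nothing under neoadjuvant treatment, surgery or surveillance. The Visit 4 mark carries the chart-review footnote, but that footnote covers imaging, planned treatment and outcomes, not adverse events. SAP 10.7.1 itself restates the window. This stands as a reasonable reading. It does not remove the ambiguity, because the appendix says any SAE and a site filing a report sees no limit there.

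Three stronger inferences are tempting, and the documents do not support them.

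- A reader might infer that late drug-related SAEs can go unreported. Section 7.2.1 makes them reportable at any time.
- A reader might infer that the sponsor loses data needed for an aggregate causality review. Section 7.2.3 only lists FDA examples of causality evidence; it does not plan such a review.
- A reader might treat the SAE sentence in Protocol 8.2 as a further conflict over scope. It describes tabulating collected data and sets no collection period.

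It is also fair to say that the SAP describes conduct in the past tense, so new protocol wording may come too late to change what sites entered.

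**Conclusion.** The concern holds in a limited form. Reporting scope is unclear only for out-of-window SAEs not suspected to be related. Separately, SAP 10.7.1 counts any out-of-window event that is entered, although Protocol 5.2.4 defines a 24-hour endpoint, and SAP Section 8 does not record this as a change.

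The exposed period is long relative to the window: up to 35 days after the pre-surgical scan against 1 day, or 3 at most, plus the neoadjuvant period in Cohort 2. How many events fall there cannot be derived. The documents give no rate of serious surgical or neoadjuvant events and do not show that sites in fact followed different readings. A reader might infer a large inflation of the serious TEAE rate; that would rest on an assumed event rate. One out-of-window SAE is enough for the table to differ from the endpoint.

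The consequence is confined to a secondary safety summary. The primary sensitivity analysis is untouched.

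**What to change.** In SAP 10.7.1, derive an in-window/out-of-window flag for each adverse event from the date and time of each injection and the event's onset. Show in-window and out-of-window events separately in the serious and fatal TEAE tables, and label the in-window rows as the Protocol 5.2.4 endpoint. This recovers the endpoint whatever sites entered. Three details need stating:

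- Protocol 7.2.4 requires an onset date but not a time. Where only the date exists, the flag works to the day.
- Onsets between 24 and 72 hours should stay identifiable, since 7.2.1 allows the extension and 5.2.4 does not mention it.
- Events with an imputed onset should be marked. SAP Table 6 moves a partial date in the month of first dosing to the dosing date, which would place the event in window by rule.

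Also reconcile Protocol 7.2.1, 7.2.3 and Appendix 1 so that they state one SAE scope; which scope to keep is for the sponsor. At the same time, correct the reference in 7.2.3 to section 8.2 for the serious criteria: 8.2 is the safety analysis, and the definition is in 7.2.2. If data collection is over, this becomes a clarification for the record and the SAP change carries the benefit.

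The cost is one derived variable, extra table rows, and day-level resolution for some events.

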11.2. Appendix 2: Eastern Cooperative Group (ECOG) Performance Status Scale

ECOG PERFORMANCE STATUS*	
Grade	ECOG
0	Fully active, able to carry on all pre-disease performance without restriction
1	Restricted in physically strenuous activity but ambulatory and able to carry out work of a light or sedentary nature, e.g., light housework, office work
2	Ambulatory and capable of all selfcare but unable to carry out any work activities. Up and about more than 50% of waking hours
3	Capable of only limited selfcare, confined to bed or chair more than 50% of waking hours
4	Completely disabled. Cannot carry on any selfcare. Totally confined to bed or chair
5	Dead

* From ECOG, [name], Group Chair

11.3. Appendix 3: Response Evaluation Criteria in Solid Tumors (RECIST 1.1) QUICK REFERENCE

11.3.1. Eligibility

Only patients with measurable disease at baseline should be included in protocols where objective tumor response is the primary endpoint. Measurable disease is defined as the presence of at least one measurable lesion.

11.3.2. Methods of Assessment

The same method of assessment and the same technique should be used to characterize each identified and reported lesion at baseline and during follow-up.

- CT is the best currently available and reproducible method to measure lesions selected for response assessment. MRI is also acceptable in certain situations (e.g., for body scans but not for lung).
- Lesions on a chest X-ray may be considered measurable lesions if they are clearly defined and surrounded by aerated lung. However, CT is preferable.
- Clinical lesions will only be considered measurable when they are superficial and ≥ 10 mm in diameter as assessed using calipers. For the case of skin lesions, documentation by color photography, including a ruler to estimate the size of the lesion, is recommended.
- Ultrasound (US) should not be used to measure tumor lesions.
- Tumor markers alone cannot be used to assess response. If markers are initially above the upper normal limit, they must normalize for a patient to be considered in complete response.
- Cytology and histology can be used in rare cases (e.g., for evaluation of residual masses to differentiate between Partial Response [PR] and Complete Response [CR] or evaluation of new or enlarging effusions to differentiate between Progressive Disease [PD] and Response/Stable Disease [SD]).
- Use of endoscopy and laparoscopy is not advised. However, they can be used to confirm complete pathological response.

11.3.3. Baseline Disease Assessment

All baseline evaluations should be performed as closely as possible to the beginning of treatment and never more than 4 weeks before the beginning of the treatment.

Measurable Lesions - Must be accurately measured in at least one dimension (longest diameter in the plane of measurement is to be recorded) with a minimum size of:

- 10 mm by CT scan (CT scan slice thickness no greater than 5 mm; when CT scans have slice thickness > 5 mm, the minimum size should be twice the slice thickness).
- 10 mm caliper measurement by clinical exam (lesions which cannot be accurately measured with calipers should be recorded as non-measurable).
- 20 mm by chest X-ray.
- Malignant lymph nodes
 - To be considered pathologically enlarged and measurable, a lymph node must be ≥ 15 mm in short axis when assessed by CT scan (CT scan slice thickness is recommended to be no greater than 5 mm). At baseline and in follow-up, only

the short axis will be measured and followed.

- Lytic bone lesions or mixed lytic-blastic lesions with identifiable soft tissue components that can be evaluated by cross-sectional imaging techniques such as CT or MRI can be considered measurable if the soft tissue component meets the definition of measurability described above.
- ‘Cystic lesions’ thought to represent cystic metastases can be considered measurable if they meet the definition of measurability described above. However, if non-cystic lesions are present in the same patient, these are preferred for selection as target lesions.

Non-Measurable Lesions - Non-measurable lesions are all other lesions, including small lesions (longest diameter <10 mm or pathological lymph nodes with 10 to <15 mm short axis), as well as truly non-measurable lesions. Lesions considered truly non-measurable include: leptomeningeal disease, ascites, pleural or pericardial effusion, inflammatory breast disease, lymphangitic involvement of skin or lung, abdominal masses/abdominal organomegaly identified by physical exam that is not measurable by reproducible imaging techniques.

Blastic bone lesions are non-measurable.

Lesions with prior local treatment, such as those situated in a previously irradiated area or in an area subjected to other loco-regional therapy, are usually not considered measurable unless there has been demonstrated progression in the lesion. Study protocols should detail the conditions under which such lesions would be considered measurable.

11.3.4. Target Lesions

- All measurable lesions up to a maximum of two lesions per organ and five lesions in total, representative of all involved organs, should be identified as target lesions and recorded and measured at baseline.
- Target lesions should be selected on the basis of their size (lesions with the longest diameter) and be representative of all involved organs, as well as their suitability for reproducible repeated measurements.
- All measurements should be recorded in metric notation using calipers if clinically assessed.

A sum of the diameters (longest for non-nodal lesions, short axis for nodal lesions) for all target lesions will be calculated and reported as the baseline sum diameters, which will be used as reference to further characterize any objective tumor regression in the measurable dimension of the disease. If lymph nodes are to be included in the sum, only the short axis will contribute.

11.3.5. Non-Target Lesions

All lesions (or sites of disease) not identified as target lesions, including pathological lymph nodes and all non-measurable lesions, should be identified as non-target lesions and be recorded at baseline. Measurements of these lesions are not required and they should be followed as ‘present’, ‘absent’ or in rare cases, ‘unequivocal progression’.

11.3.6. Response Criteria Evaluation of target lesions

Complete Response (CR)	Disappearance of all target lesions. Any pathological lymph nodes (whether target or non-target) must have reduction in short axis to <10 mm.
Partial Response (PR)	At least a 30% decrease in the sum of the diameters of target lesions, taking as reference the baseline sum of diameters
Progressive Disease (PD)	At least a 20% increase in the sum of the LD of target lesions, taking as reference the smallest sum on study (this may include the baseline sum). The sum must also demonstrate an absolute increase of at least 5 mm
Stable Disease (SD)	Neither sufficient shrinkage to qualify for PR nor sufficient increase to qualify for PD

Special notes on the assessment of target lesions

- Lymph nodes identified as target lesions should always have the actual short axis measurement recorded even if the nodes regress to below 10 mm on study. When lymph nodes are included as target lesions, the ‘sum’ of lesions may not be zero even if complete response criteria are met since a normal lymph node is defined as having a short axis of <10 mm.
- Target lesions that become ‘too small to measure’. While on study, all lesions (nodal and non-nodal) recorded at baseline should have their actual measurements recorded at each subsequent evaluation, even when very small. However, sometimes lesions or lymph nodes become so faint on a CT scan that the radiologist may not feel comfortable assigning an exact measure and may report them as being ‘too small to measure’, in which case a default value of 5 mm should be assigned.
- Lesions that split or coalesce on treatment. When non-nodal lesions ‘fragment’, the longest diameters of the fragmented portions should be added together to calculate the target lesion sum. Similarly, as lesions coalesce, a plane between them may be maintained that would aid in obtaining maximal diameter measurements of each individual lesion. If the lesions have truly coalesced such that they are no longer separable, the vector of the longest diameter in this instance should be the maximal longest diameter for the ‘coalesced lesion’.

11.3.7. Evaluation of non-target lesions

Complete Response (CR)	Disappearance of all non-target lesions and normalization of tumor marker levels. All lymph nodes must be non-pathological in size (< 10 mm short axis)
Non-CR/Non-PD	Persistence of one or more non-target lesion(s) or/and maintenance of tumor marker level above the normal limits
Progressive Disease (PD)	
Unequivocal progression of existing non-target lesions.
 
When patient has measurable disease. To achieve ‘unequivocal progression’ on the basis of the non-target disease, there must be an overall level of substantial worsening in non-target disease such that, even in presence of SD or PR in target disease, the overall tumor burden has increased sufficiently to merit discontinuation of therapy. A modest ‘increase’ in the size of one or more non-target lesions is usually not sufficient to qualify for unequivocal progression status
 
• When patient has only non-measurable disease. There is no measurable disease assessment to factor into the interpretation of an increase in non-measurable disease burden. Because worsening in non-target disease cannot be easily quantified, a useful test that can be applied is to consider if the increase in overall disease burden based on change in non-measurable disease is comparable in magnitude to the increase that would be required to declare PD for measurable disease. Examples include an increase in apleural effusion from ‘trace’ to ‘large’ or an increase in lymphangitic disease from localized to

widespread.

New Lesions

The appearance of new malignant lesions denotes disease progression:

- The finding of a new lesion should be unequivocal (i.e., not attributable to differences in scanning technique, change in imaging modality or findings thought to represent something other than tumor, especially when the patient's baseline lesions show partial or complete response).
- If a new lesion is equivocal, for example because of its small size, continued therapy and follow-up evaluation will clarify if it represents truly new disease. If repeat scans confirm there is definitely a new lesion, then progression should be declared using the date of the initial scan.
- A lesion identified on a follow-up study in an anatomical location that was not scanned at baseline is considered a new lesion and disease progression.

11.3.8. [¹⁸F]FDG-PET

It is sometimes reasonable to incorporate the use of [¹⁸F]FDG-PET scanning to complement CT in assessment of progression (particularly possible 'new' disease). New lesions on the basis of [¹⁸F]FDG-PET imaging can be identified according to the following algorithm:

Negative [¹⁸F]FDG-PET at baseline, with a positive [¹⁸F]FDG-PET at follow-up is PD based on a new lesion.

No [¹⁸F]FDG-PET at baseline and a positive [¹⁸F]FDG-PET at follow-up:

- If the positive [¹⁸F]FDG-PET at follow-up corresponds to a new site of disease confirmed by CT, this is PD.
- If the positive [¹⁸F]FDG-PET at follow-up is not confirmed as a new site of disease on CT, additional follow-up CT scans are needed to determine if there is truly progression occurring at that site (if so, the date of PD will be the date of the initial abnormal [¹⁸F]FDG-PET scan).
- If the positive [¹⁸F]FDG-PET at follow-up corresponds to a pre-existing site of disease on CT that is not progressing on the basis of the anatomic images, this is not PD.

